### **C11. Sample Size Calculation and Power Analyses.**

For sample size calculations, preliminary data from [name] and colleagues were used. In [name] and colleagues, participants in GMI attended a significantly higher number of outpatient SUD treatment sessions compared to their counterparts in TAU. Using zero inflated negative binomial regression (ZINB) and accounting for group level nesting, at 3-month follow-up, participants in GMI attended significantly more outpatient mental health treatment sessions compared to TAU,  $b = .944 (.307)$ ,  $t = 3.079$ ,  $p < .001$ ; Cohen's  $d = .54$ . The efficacy of GMI relative to TAU for lowering substance was assessed among the same sample of dually diagnosed Veterans using ZINB. At 3-month follow-up, participants in GMI consumed significantly less alcohol in standard drinks ( $b = -155.3 (70.9)$ ,  $t = -2.19$ ,  $p = .03$ ; Cohen's  $d = .36$ ) and drank fewer standard drinks in terms of peak (highest) alcohol drinking day ( $b = -4.78 (2.03)$ ,  $t = -2.4$ ,  $p = .02$ ). No baseline differences between

groups were found on alcohol consumption. For comparing the longitudinal profile of the substance use outcomes (standard drinks/day, peak standard drinks/day, # drinking days, # binge drinking days) using repeated measures analysis assuming 3 measurement time points, level of significance  $\alpha=0.05$ , two-tailed comparison, correlation between pairs of measurements within participants no larger than  $\rho=0.5$ , we estimate that 50 participants per group (total  $n=100$ ) are needed to achieve a power of 89% to detect a difference of 0.5 standard drinks between GMI and CT. A sample size of 65 ( $n=130$ ) will provide 83% power to detect a difference of 0.4 standard drinks between treatment conditions. The corresponding sample size requirements after adjusting for a 30% dropout rate are 142 (71 per group) and 186 (93 per group), respectively. To account for the “fraction of missing” information that must be imputed in the intent-to-treat (ITT) sample and the dilution effect of ITT analyses, we further inflate the sample size by 30% to achieve a final ITT sample size of 93 participants randomized to GMI and CT (total  $N = 186$ ) to detect a difference of 0.4 standard drinks between treatment conditions. For the global statistical test (GST), when the collection of outcomes (e.g., standard drinks/day, etc.) show consistent directionality with regard to improvement, GST will have higher power than that of tests of single outcomes.

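### C11 states its detectable differences in standard drinks with no SD, although the powers fit SD units, and the second 30% inflation it announces is not contained in the 93 per arm

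*Combined protocol and SAP*

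**What the plan says.** C11 bases the sample size on a "repeated measures analysis assuming 3 measurement time points", two-sided alpha 0.05, with the "correlation between pairs of measurements within participants no larger than" 0.5. No correlation structure and no SD are given. The comparison covers the "substance use outcomes (standard drinks/day, peak standard drinks/day, # drinking days, # binge drinking days").

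Two cases are stated. With 50 per arm, power is 89% for a difference of 0.5 standard drinks. With 65 per arm, the design "will provide 83% power to detect a difference of 0.4 standard drinks between treatment conditions".

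On losses, C11 says: "The corresponding sample size requirements after adjusting for a 30% dropout rate are 142 (71 per group) and 186 (93 per group), respectively". The next sentence refers to information that must be imputed and to dilution under ITT, and adds: "we further inflate the sample size by 30% to achieve a final ITT sample size of 93 participants randomized to GMI and CT". It names the 0.4 case again and the total of 186. Section C3 (Attrition and Retention) describes the same 186 as allowing for up to 30% loss to follow-up and mentions no second allowance.

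Two other sections bear on what the power refers to. C12d makes month 1 the primary time point for the contrasts of means. C5 randomises recruitment weeks, so that everyone entering in a given week joins the same closed group.

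**The concern.** A detectable difference in drinks can be interpreted only with an SD in drinks. Without one, the reader cannot tell whether 0.4 is a number of drinks or a fraction of an SD. The label also cannot be literally right for drinking days and binge-drinking days.

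The second inflation is a separate problem. The number is already 93 for the 0.4 case when C11 says it is inflated by a further 30%, and it is still 93 afterwards.

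The stake is interpretation. A null result, or an effect reported in drinks, would be judged against a detectable difference that the calculation probably never used. A reader would also credit the trial with a reserve for imputed data and ITT dilution that it does not have.

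**Working it through.** **1. Reproducing the stated powers.** Inputs from C11: alpha 0.05 two-sided, three visits, correlation at most 0.5, 50 or 65 per arm, differences 0.5 or 0.4. Assumptions: SD = 1, the endpoint is the mean of three visits, participants are independent, and there is no baseline adjustment. The test is a two-sample noncentral t with 2n − 2 degrees of freedom and noncentrality d / √(2v/n), where v is the variance of the three-visit mean in units of SD².

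- Compound symmetry (CS): v = (1 + 2ρ)/3, which is 0.667 at ρ = 0.5, 0.600 at 0.4 and 0.333 at 0.
- AR(1), ρ = 0.5: v = (3 + 4 × 0.5 + 2 × 0.25)/9 = 0.611.

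| Structure | Power, n = 50, d = 0.5 (stated 89%) | Power, n = 65, d = 0.4 (stated 83%) | SD that gives the stated powers |
|---|---|---|---|
| AR(1), ρ = 0.5 | 88.6% | 82.5% | 0.99 |
| CS, ρ = 0.4 | 89.2% | 83.2% | 1.00 |
| CS, ρ = 0.5 | 85.8% | 79.2% | 0.95 |
| ρ = 0 | 99.0% | 97.5% | 1.35 |

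Within each row the two stated powers require the same SD. Over the correlations that C11 permits, that SD runs from 0.95 to 1.35, and it is almost exactly 1 under AR(1) 0.5 or CS 0.4.

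**2. Comparison with the pilot scale.** C11 reports that pilot GMI participants "drank fewer standard drinks in terms of peak (highest) alcohol drinking day", with b = −4.78 and SE 2.03. If the SE is treated as that of a simple difference between two means:

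- 59 per arm: SD ≈ 2.03/√(2/59) = 11.0 drinks.
- 51 per arm (59 × 0.87, using the 13% drop-out in C3): SD ≈ 2.03/√(2/51) = 10.3 drinks.

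On that scale 0.4 SD is about 4 drinks (0.4 × 10.3 = 4.1; 0.4 × 11.0 = 4.4), and a literal 0.4 drinks is about 0.04 SD. This is rough. The coefficient comes from a zero-inflated negative binomial analysis. The companion engagement analysis is described as "Using zero inflated negative binomial regression (ZINB) and accounting for group level nesting", so the SE may include nesting. The pilot sample all had an alcohol disorder. The documents give no SD for standard drinks per day.

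**3. The allowance.**

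- 50/0.7 = 71.4 (stated 71) and 65/0.7 = 92.9 (stated 93). One 30% allowance gives both stated figures.
- A second 30% on the 0.4 case: 93 × 1.3 = 120.9, or 65/(0.7 × 0.7) = 132.7. That is 121 to 133 per arm.
- The only two-step route to 93 is 71 × 1.3 = 92.3. It starts from the 0.5 case, whereas the sentence names 0.4.

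**4. Power at one visit, for scope only.** With v = 1, 0.4 SD, no baseline adjustment and no clustering:

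| Per arm | Basis | Power |
|---|---|---|
| 65 | 30% loss | 61.9% |
| 81 | 13% loss (93 × 0.87 = 80.9) | 71.6% |
| 93 | no loss | 77.4% |

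**The case against.** The strongest reply is that the power figures are sound. C11 sets only an upper bound of 0.5 on the correlation. AR(1) with 0.5 has pairwise correlations of 0.5, 0.5 and 0.25, which meets that bound, and it reproduces both powers. C12b names AR(1), though for the analysis model rather than for the sample size. This stands. A reader might set CS at 0.5 (79% and 86%) against the stated values and infer an arithmetic error. The documents do not support that, because they never specify CS at 0.5.

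Second, C11 reports the pilot effects as Cohen's d of 0.54 and 0.36, so an alert reader could guess that 0.5 and 0.4 are standardised. This supports the inference, but the text still says standard drinks.

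Third, the pilot SD is a proxy taken from a model coefficient for a peak-day outcome. This also stands. It is enough to show that an SD of 1 drink is implausible for peak drinks, and not enough to derive a power for this trial.

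Fourth, C11 speaks of a longitudinal profile, and the three-visit mean is a reconstruction. That is so, but it is a simple reading that returns both stated figures, and C11 mentions neither month 1 nor any allowance for clustering.

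Finally, C3 already describes 186 as a 30% loss allowance. That confirms the single allowance and leaves the sentence in C11 unreconciled.

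**Conclusion.** Two stated properties of the design need correction, and neither calls for a different N.

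**Unit.** The differences of 0.5 and 0.4 are most likely SD units mislabelled as drinks. This rests on the powers reproducing with an SD of 1 under structures that C11 allows. For peak drinks, 0.4 SD may be about 4 drinks, roughly ten times the printed figure, subject to the limits of the pilot SE.

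**Allowance.** This part needs no assumption. The 93 per arm holds one 30% allowance, and the claimed reserve for imputation and ITT dilution does not exist.

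Three stronger conclusions are tempting but not supported:

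- That the trial has almost no power. This takes 0.4 drinks literally against a rough SD; it shows why the literal reading fails and says nothing reliable about the trial's power.
- That the trial needs 121 to 133 per arm. Those figures show only what the sentence would imply if it were carried out.
- That power at month 1 is 62%. That value assumes the whole 30% loss by month 1 and no baseline adjustment. The documents give no ICC, so the effect of clustering cannot be quantified from them.

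**What to change.** Keep N at 186 and reword the C11 paragraph:

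1. Relabel the targets as 0.4 SD and 0.5 SD, or state the SD used and give the equivalent in each outcome's own unit, including the two day counts.
2. State the correlation structure and value that give 83% and 89%.
3. Delete the sentence on further inflation. Say that 93 per arm covers 30% loss only, with no separate reserve for ITT dilution.
4. State that the power refers to the repeated-measures comparison over three visits with independent participants. Say that it is not the power at the month-1 primary time point (C12d) or under clustering by group (C5). If a month-1 figure is added, give it as conditional: for 0.4 SD with no baseline adjustment and no clustering, about 62% at 65, 72% at 81 and 77% at 93 per arm.

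The cost is one paragraph of rewording, with no change to any analysis. The downside is that the stated power becomes conditional and looks less favourable.

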## **C12. Overview of the statistical analysis plan.**

**Effectiveness analyses:** all health services and participant outcomes (see section C9) will be obtained at three time points (month 1, 3 and 6-months post-randomization). These variables include: (a) Substance use outcomes (e.g., standard drinks/day (SEC), peak standard drinks/day, # drinking days, # binge drinking days, # illicit drug use days, etc.); (b) Treatment engagement (e.g. # of substance abuse/mental health treatment sessions attended, # AA sessions attended, # AA sponsor contacts; (c) Psychosocial adjustment (social support, community participation) and (d) Quality of life/psychiatric indices (QOLS, SF-12, BSI-18); (e) Engagement in structured/productive work activities (% of days each month engaged in work or volunteer activities); (c) Process measures (CPOSS-VA, HAQ) will be assessed at 1-month follow up.

**Analysis sets.** The ITT sample comprises all randomized participants. The per-protocol/completer sample comprises participants who are compliant with protocol requirements and for whom all required measurements have been made. Primary analyses will be carried out using the ITT analysis set.

**C12a. Premature exits (study drop-outs) and missing data.** We will employ longitudinal data methods (generalized linear mixed models [GLMM]), which allow for missing at random (MAR) data. Analyses will be carried out separately for the ITT and per protocol samples to test sensitivity of conclusions to study drop-outs/non-adherence. For dichotomous outcomes, in additional “worst case” sensitivity analyses, we will assume that missing data are “failures” (non-successes), e.g. in calculating # of days not using alcohol, we will assume that missing entries in daily log regarding alcohol use are days in which alcohol was used. In addition, to understand the missing data and study drop-out process, we will fit a missing data model with a dichotomous outcome (1=missing, 0=not missing) using logistic regression. We will also use information on study drop-outs as one of the feasibility (process) outcome measures of the interventions being compared. To investigate potential limits on generalizability, we will compare characteristics of the non-completers/non-compliers with the completer/protocol adherent groups. These comparisons will be carried out for the total group and within treatment allocations. To describe potential bias due to missing observations, we will carefully document reasons for missing data. We will use this information to manage and correct for potential bias that could arise from informative study drop-out.

**C12b. Measurement error:** to account for measurement error we will put a structure into the R-side matrix of the GLMM. Given that deviating from the diagonal R matrix adds complexity to model fitting, we will try AR(1) and CS covariance structures to parsimoniously account for measurement error.

**C12c. Multiple outcome variables.** We acknowledge concern about inflation of Type I error. This concern must be balanced with the need to avoid overly conservative Type I (false positive) error rates that may result in excessively high Type II (false negative) error rates. As a standard method of balancing these concerns, we will use multivariate GLMM to jointly model the correlated outcomes and study the relationship between the multiple outcomes and treatment. For each outcome ( $Y_{ij}$ ), we consider the model,  $E(Y_{ijk} | X_{ij}(t), Z_{ij}) = g^{-1}(X_{ij}(t)\beta_k + Z_{ij}b_{ik})$ , where  $g$  is a monotone link function,  $b_{ik} \sim N(0, G_k)$  and  $Y_{ij}$  is the response for the  $i$ th subject at the  $j$ th time with  $n_i$  ( $n_i-1, \dots, 10$ ) repeated measurements,  $X_{ij}$  and  $Z_{ij}$  represent vectors of fixed and random effect covariates, respectively, and  $G$  is the covariance matrix for  $b_i$ . If  $b_i$  is a vector of random intercept and slope, it indicates that there is natural heterogeneity among individuals in both their baseline level and changes in the expected outcomes over time. In addition to the variability in the random effects, a diagonal R-side covariance matrix of the form  $2\ln$  is included to account for random error. When the random error is suspected to have more measurement error than what is typically expected then we will use AR(1) R-side covariance matrix. Additional

sensitivity analysis will be made to balance between model complexity and reduction in bias. We will use Poisson distribution with a log-link for count outcomes (e.g., # drinking/drug use days, # days SUD treatment, # days structured work activities), Binomial distribution with logit-link for binary outcomes (e.g. attended treatment/did not attend treatment) and Gaussian distribution with identity-link for continuous outcomes (e.g., standard drinks). When we suspect over-dispersion in the count models that is beyond what is assumed by the Poisson GLMM then we will use Negative Binomial distribution. To deal with zero inflation, we will use zero-inflated Poisson (ZIP) and negative binomial (ZINB) models. For multiple outcomes, we will use a joint model based on linking the GLMM models for each outcome type by assuming a joint statistical distribution for the random coefficients (intercept and slopes). Let  $Y_{ijk}$  be the response from the  $k$ th outcome for subject  $i$  at occasion or time  $j$  ( $i=1, \dots, n$ ;  $k=1, \dots, K$ ;  $j=1, 2, \dots, n_i$ ). The GLMM can be given as,  $E(Y_{ijk} | X_{ij}(t), Z_{ij}) = g^{-1}(X_{ij}(t)\beta_k + Z_i b_{ik})$ , where  $b_{ik} \sim N(0, G_k)$  and  $X_i$  and  $Z_i$  represent vectors of fixed and random effect covariates, respectively, and  $G_k$  is the covariance matrix for  $b_{ik}$ . We will use a random coefficient model with shared random intercept and random slope for each outcome. The resulting 'over all' covariance matrix (D) from this model will provide standard error estimates that account for correlation among the multiple outcomes. A key assumption for these models is conditional independence where the responses are independent given the random effects. These models can be fitted using Proc NLMIXED or GLIMMIX in SAS v9.3.

**C12d. Analysis plan for Clinical, Social, and Quality of Life outcomes (Specific AIM I; Hypotheses 1 through 4):** To evaluate the relative efficacy of (a) GMI and (b) CT on (a) five health services outcomes (i) substance use (ii) treatment engagement, (iii) psychosocial integration (e.g., social support, community participation), (iv) quality of life/psychiatric indices, and (v) # of days engaging in structured/productive work activities. The longitudinal trajectory of efficacy outcomes will be compared using the GLMM approach, which accommodates missing at random (MAR) data and a wide range of data types/distributional assumptions: counts (e.g., # AA sessions, # times talking with AA sponsor, # substance abuse treatment sessions attended); dichotomous (e.g., abstinent/not abstinent), proportions (proportion days not drinking alcohol or using illegal drugs), and ordinal (e.g. CPOSS-VA, QOLS). When the number of zeroes is in excess of what is normally expected from a poisson model, we will fit GLMM to accommodate zero-inflation. We will use negative binomial regression to deal with over dispersion. Logit link for dichotomous outcomes, log link for count outcomes will be considered. The basic modeling procedure involves using the longitudinal outcome measurements within each of the domains separately as the dependent (outcome) variable, with intervention group (fixed effect), time (random effect), and time by intervention as the primary independent variables. In further multivariable modeling, additional covariables (as appropriate for a given dependent variable) will be added to the basic model to adjust for potential confounding effect of these variables. GLMM accommodates both fixed and time-varying covariates. For example, for the treatment engagement variable, the # of AA sessions measured monthly for 6 months will be an outcome variable, intervention group (GMI, CT), time, and time X intervention will be the primary independent variables in the basic (unadjusted) model, and psychiatric comorbidity (number and severity), age, race, and gender will be added in the subsequent (adjusted) model to adjust for the possible confounding effect of these variables. Unadjusted and covariate-adjusted least squares means for each outcome variable will be compared at the primary time point (month 1) and at intermediate secondary time points (months 3 and 6) using appropriate model contrasts and the Tukey-Kramer adjustment for multiple comparisons for the secondary time points. These contrast comparisons, along with corresponding 95% CI, will provide estimates of the difference in outcome means (effect sizes) for the hypothesized comparisons. For longitudinal dichotomous outcomes (e.g., maintenance of sobriety), we will compare unadjusted and covariate-adjusted proportions across the longitudinal trajectory (at 1, 3 and 6 months) for GMI and CT. For the end-of-active treatment time point, this analysis is equivalent to a logistic regression analysis.

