patients and collaterals were interviewed at 1 and 3-month follow-up. Three main outcomes of the pilot study showed that: 1) GMI reduced the number of inpatient hospital detoxification re-admissions after initial hospitalization compared to ST: GMI participants were re-admitted to inpatient detoxification fewer times (GMI: 6.8%; ST: 25.6%;  $p = .03$ ) during the 3-month follow-up period; 2) Participants in GMI attended more outpatient aftercare treatment sessions compared to participants in ST ( $M=5.7$  [SD=6.7] vs.  $M=2.5$  [1.9];  $p=.001$ ) and attended more 12-Step or AA/NA self-help sessions ( $M=21.7$  [18.8] vs.  $M=6.8$  [6.8];  $p<.01$ ) by 3-month follow-up; and 3) GMI was associated with reduced substance use: Participants in GMI drank less alcohol (measured in standard ethanol content units), compared to their counterparts in ST by 3-month follow-up ( $M=117.3$  [182.8] vs.  $M=262.3$  [312.9],  $p=.04$ ), engaged in less binge drinking ( $M=4.6$  [3.2] vs.  $M=13.9$  [10.5],  $p=.001$ ) and had fewer days of illicit drug use ( $M=5.2$  [7.2] vs.  $M=13.0$  [12.0];  $p=.01$ ) at 1-month follow-up. A smaller *proportion* of GMI participants reported binge drinking (34.1% in GMI vs. 55.8% in ST,  $p = .02$ ) at the 3-month follow-up.

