**II. Project 2: GMI resulted in lower alcohol use, higher outpatient treatment attendance, and greater participant change talk compared to TAU**. In her CDA-2 (CDA-2-016-08S) titled: ‘Impact of Group Motivational Interviewing on Dually Diagnosed Veterans’, [name] compared GMI to treatment-as-usual (TAU) among 118 Veterans with current alcohol dependence or abuse, an accompanying drug abuse disorder, and a co-existing Axis I psychiatric disorder recruited through the Charleston VAMC Substance Abuse Treatment Center (SATC). Participants were randomized to GMI ( $n=59$ ) or TAU ( $n=59$ ). All participants were interviewed at 1 and 3-month follow-up. Patients attended four 75- minute sessions of GMI or TAU across 4 consecutive days. TAU was designed as a psycho-educational group (e.g., addiction as a chronic disease). [name] modified her GMI protocol for application in the VA outpatient SATC, trained five clinicians to provide interventions, and provided consultation for continued therapist adherence/competence to the protocol. Participant characteristics and DSM-IV-TR substance use and comorbid Axis I diagnoses are listed in Tables 1 and 2. A study coordinator blind to study conditions evaluated participants at baseline and at a 1 and 3-month follow-up. Treatment utilization was assessed via CPRS. Researchers counted the number of outpatient substance abuse treatment encounters and individual mental health treatment appointments with mental health staff (e.g., case-managers, psychiatrists, psychologists) that occurred in the 3 months following the patient’s consent (at the Charleston VAMC only). Substance use was assessed using the Time-Line Follow Back. We measured daily and peak alcohol consumption in standard drinks at 3-month follow-up. Data analyses were conducted using ANCOVA with ZINB distribution. Although analyses remain ongoing, preliminary results for primary outcome variables reveal the following: **A) Participants in GMI attended significantly more general outpatient mental health treatment sessions compared to TAU** by 3-month follow up,  $b = .944$  (.307),  $t = 3.079$ ,  $p < .001$ ; Cohen’s  $d=.54$ . No baseline differences in treatment engagement were found.

| Table 2. DSM-IV-TR Substance Use             | GMI   | TAU   |
|---|--------------|--------------|
| Alcohol Abuse/dependence                            | 59
(100%) | 59
(100%) |

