#### **6. Data Monitoring and Safety Plan**

Data Management and Analysis: A data analysis plan is outlined in the Data Analysis section. Briefly, the primary outcomes are (Hypothesis 1): Substance use (e.g. standard drinks, peak standard drink day, # drinking days, drinks per drinking day, binge drinking days, # illicit drug use days, etc); and (b) Treatment engagement (e.g. number of substance abuse/mental health treatment sessions attended, # AA sessions attended, # AA sponsor contacts).

Secondary outcome measures will be: (c) Psychosocial adjustment (Hypothesis 2; social support, community participation); (d) Quality of life/psychiatric indices (Hypothesis 3; QOLS, SF-12, BSI-18); (e) Engagement in structured/productive work activities (Hypothesis 4; percent of days each month engaged in work or volunteer activities); and (c) Process measures (CPOSS, HAQ) will be assessed at post-treatment (1-month follow up).

The longitudinal trajectory of efficacy outcomes will be compared using the generalized linear mixed models (GLMM) approach. GLMM accommodates missing at random (MAR) data and a wide range of data types/distributional assumptions: counts (e.g., # AA sessions, # times talking with AA sponsor, # substance abuse treatment sessions attended); dichotomous (e.g., abstinent/not abstinent), proportions (proportion days not drinking alcohol or using illegal drugs), ordinal (e.g. CPOSS-VA, QOLS). When the number of zeroes is in excess of what is normally expected from a poisson model, we will fit GLMM that can accommodate zero-inflation. We will use negative binomial regression to deal with over dispersion. Unadjusted and least squares adjusted means from the GLMM contrast comparisons, along with corresponding 95% CI, will provide estimates of the difference in outcome means (effect sizes) for the hypothesized comparisons. For longitudinal dichotomous outcomes (e.g., maintenance of sobriety), we will compare unadjusted and covariate-adjusted proportions across the longitudinal trajectory (at 1, 3 and 6 months) for the intervention groups using GLMM for a binary outcome. For the end-of-active treatment time point, this analysis is equivalent to a logistic regression analysis.

Quality Assurance: Data quality will be monitored by random inspection of the completed forms by research staff and any irregularities or problems detected will be discussed with the PI. Therapists will receive standardized

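### Standard drinks: the Gaussian identity-link model, with no baseline-drinking covariate named, is valid but probably inefficient for a skewed H1 measure

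*Combined protocol and SAP*

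**What the plan says.** - **Model.** C12c assigns standard drinks a "Gaussian distribution with identity-link for continuous outcomes (e.g., standard drinks"). The negative binomial fallback in that section opens "When we suspect over-dispersion in the count models". The next sentence reads "To deal with zero inflation, we will use zero-inflated Poisson (ZIP) and negative binomial (ZINB) models" and names no outcome. C12d sets its trigger against a count model: "When the number of zeroes is in excess of what is normally expected from a poisson model, we will fit GLMM to accommodate zero-inflation".
- **Covariates.** The basic model in C12d has arm, time and their interaction. The adjusted example adds psychiatric comorbidity and demographics. Baseline drinking appears in neither, although Table 4 schedules the TLFB at baseline.
- **Role of the outcome.** The Data Monitoring and Safety Plan says "the primary outcomes are (Hypothesis 1): Substance use (e.g. standard drinks, peak standard drink day" and continues with further measures, so standard drinks is one member of a family. C11 states its detectable differences in standard drinks.
- **Earlier data.** C2a reports the pilot: "Participants in GMI drank less alcohol (measured in standard ethanol content units"), with mean 117.3 [SD 182.8] against 262.3 [312.9]. For the later trial, C2 (Project 2) says "Data analyses were conducted using ANCOVA with ZINB distribution", and C11 says "The efficacy of GMI relative to TAU for lowering substance was assessed among the same sample of dually diagnosed Veterans using ZINB".

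**The concern.** Drinks cannot be negative. An SD larger than the mean therefore implies a long right tail, in which a few heavy drinkers supply most of the variance of a difference in means. Drinking also tends to be stable within a person on a proportional scale, so baseline drinking can remove more noise under a log link than under an identity link. The plan uses neither feature for this outcome. It also does not explain why it leaves the method that it reports for the earlier trial. What is at stake is precision on the measure used to size the trial, and a model choice that would otherwise be made after the data are seen.

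**Working it through.** **1. Skew.** SD/mean is 182.8/117.3 = 1.56 in the GMI arm and 312.9/262.3 = 1.19 in the standard-treatment arm.

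**2. The plan's own power.** C11 gives no SD, so an SD of 1 is assumed. The mean of T = 3 measurements with correlation ρ = 0.5 has SD √[(1 + 2ρ)/3] = √(2/3) = 0.816. Power is Φ(δ / (SD·√(2/n)) − 1.96).
- n = 65, δ = 0.4: 0.4/(0.816 × 0.1754) = 2.79, power 79.8% (stated 83%).
- n = 50, δ = 0.5: 0.5/(0.816 × 0.2) = 3.06, power 86.5% (stated 89%).
- With ρ = 0.4, which C11 also allows, the results are 83.7% and 89.8%.

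The stated figures are thus under-specified rather than shown wrong. 65/0.7 = 92.9, so 93 per arm reproduces.

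**3. Does skew spoil the Gaussian test?** Simulation of zero-inflated, over-dispersed totals with pilot-like moments (300 trials per setting, 20% zeros assumed, one time point, no baseline):
- Type I error was 5.7% at 65 per arm and 3.7% at 93.
- Power at d = 0.40 was 60% at 65 per arm (normal theory 62.6%) and 83% at 93 (77.8%). The Monte Carlo SE is up to about 3 points.

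The test holds its level and roughly its nominal power.

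**4. Is a log-link model with baseline more efficient?** Simulation of log-normal Poisson drinks with excess zeros: 500 trials per setting, SD/mean about 1.35, d about 0.32, one time point, no clustering. The documents give neither zero shares nor baseline correlations, so both are assumed. Power in %:

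| Per arm | Zeros, CT / GMI | Log-scale correlation | Gaussian, no baseline | Gaussian, baseline | Neg. binomial, log baseline, robust SE | Gain over adjusted Gaussian |
|---|---|---|---|---|---|---|
| 65 | 15 / 15 | 0.3 | 47 | 48 | 60 | 12 |
| 65 | 15 / 15 | 0.5 | 46 | 52 | 65 | 13 |
| 65 | 15 / 15 | 0.7 | 47 | 64 | 82 | 18 |
| 65 | 15 / 35 | 0.5 | 47 | 50 | 59 | 9 |
| 65 | 15 / 49 (all via abstinence) | 0.5 | 41 | 45 | 56 | 11 |
| 93 | 15 / 15 | 0.5 | 61 | 67 | 83 | 16 |
| 93 | 15 / 49 (all via abstinence) | 0.5 | 58 | 62 | 69 | 7 |

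These levels are not comparable with the stated 83%, because they use one time point and a smaller effect. Only the differences within a row matter. A larger run (800 trials per setting) widened the range of gains to about 6 to 20 points.

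**5. Where does the gain come from?** A separate run (600 trials, 65 per arm, 15% zeros, d about 0.35) split it:
- Distribution alone, no baseline: Gaussian 49–53%, negative binomial 55–57%, a gain of 4 to 6 points (1 to 7 in the 800-trial run).
- With baseline (raw for Gaussian, log for negative binomial): 52 vs 59% at correlation 0.3, 55 vs 67% at 0.5, 63 vs 81% at 0.7. The gains are 7, 12 and 18 points.

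At a correlation of 0.5 or more, most of the gain needs the log link and baseline together. At 0.3 in this run, little is added beyond the distribution change.

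**6. Cost in type I error.** The negative binomial model with robust SE rejected 5–6%, 5.6–5.8% and 6.8–7% of null trials across the three runs in steps 4 and 5, against 3–5% for Gaussian.

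**7. Which alternatives fail?** In the step 3 simulation at 65 per arm:
- The ZINB count coefficient had 60% power against 92% for Gaussian when zeros were 15% vs 40% (d = 0.57). It had 4% against 59% when the effect ran almost wholly through abstinence (d = 0.37).
- A negative binomial model with model-based SEs and no baseline rejected only 0.7% under the null, and had 35% power against 60% at d = 0.40. The robust SE is therefore essential.

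**8. The ZINB precedent.** The alcohol result is b = −155.3 (70.9), and 155.3/70.9 = 2.19 matches its t. As a log-link coefficient it would mean a ratio of exp(−155.3), about 4 × 10⁻⁶⁸, so it must be a difference in drinks. The engagement coefficient .944 gives exp(.944) = 2.57, which is plausible on the log scale.

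**The case against.** The case for leaving the plan alone has real weight.

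- **Flexibility exists.** The zero-inflation sentence in C12c names no outcome, and C12d mentions negative binomial regression for over-dispersion without restricting it. C12d also lets further covariates be added. This stands in part: the tools are listed, but no rule applies them to an outcome classed as continuous. It is also why the fair comparator is a baseline-adjusted Gaussian model.
- **Different variable.** The pilot figures are ethanol amounts over follow-up in psychiatric inpatients. C11 and C12 name drinks per day, which need not be an integer. This stands: the SD/mean ratio is borrowed, and a count model needs totals with an offset.
- **A difference in means matches the 0.4-drink target.** This stands, and is a reason to keep that analysis.
- **The gain rests on assumptions.** This stands. Part of it may also reflect the slightly liberal robust SE, since powers were not compared at equal size.

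Three stronger readings are tempting, and the documents support none of them. A reader might infer that the Gaussian analysis is invalid, but its type I error was at or below nominal within simulation error. A reader might infer that the trial loses power on its primary outcome. However, standard drinks is one of several H1 measures, the count measures already have count models, and no SD or zero share for drinks per day is given from which to compute a loss. A reader might also infer that returning to ZINB is the remedy. Step 7 shows the danger of that, and step 8 shows that the precedent is itself unclear.

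**Conclusion.** The point holds as a matter of efficiency and pre-specification. The Gaussian identity-link model is a valid but probably inefficient choice for standard drinks, and no baseline-drinking covariate is named. Replacing it with a negative binomial log-link model with log baseline and robust SE is worth about 6 to 20 points of power over a baseline-adjusted Gaussian model. That range assumes 65 to 93 per arm, SD/mean about 1.3, at least 15% zeros, a log-scale baseline correlation of 0.3 to 0.7, one time point and no clustering by workshop. The true gain could lie outside it if drinks per day behave differently in this population. The change is recommended; the trial's validity does not depend on it.

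**What to change.** Before unblinding, amend C12c and C12d as follows:

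1. Adjust every standard-drinks analysis for baseline drinks from the TLFB.
2. Pre-specify a negative binomial log-link mixed model for total drinks, with an offset for days observed, log baseline drinks (stating how a zero baseline is handled) and robust SE with a small-sample correction.
3. Report one treatment parameter, the ratio of overall means with abstainers included. Do not use a ZINB count coefficient as the treatment effect.
4. Keep the Gaussian difference in means, adjusted for baseline, as a sensitivity analysis, so that the 0.4-drink target can still be reported.
5. State why the model departs from the ZINB reported for the earlier trial, and clarify the scale of the −155.3 coefficient.

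This is a change of SAP wording. It needs no new data and no more participants. The downsides are that the main effect becomes a ratio, so the target must be re-expressed on that scale, and that type I error may run slightly above nominal (about 5 to 7% in simulation), which is the reason for the small-sample correction.
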